After the initial 12 weeks of study treatment, a protocol-specified corticosteroid taper will be initiated and conducted under the direction of the investigator for participants in all 3 arms. The taper will proceed with a target of reaching a prednisone equivalent dose of ≤5mg/day by Week 26. If the investigator believes the participant would benefit from continued steroid taper and, if tolerated, a prolonged corticosteroid taper should continue after Week 26 with the goal of corticosteroid discontinuation. Participants who are able to tolerate the final taper will be withdrawn from corticosteroids. If a participant is unable to tolerate the final stage of the corticosteroid taper, the investigator may reinitiate corticosteroids at a prednisone equivalent dose of up to and including 5 mg/day. If a 7-day average prednisone equivalent dose of >5 mg/day is required at any time after Week 26 visit (i.e., beginning first day of Week 27), the participant will be considered a treatment failure for the efficacy endpoints.

Anti-malarial therapies for SLE may not be initiated during the study, but may be continued or dose-adjusted during the study, and will be allowed within the definitions of

the efficacy endpoints. Switching of anti-malarial due to toxicity or lack of availability is permitted

Non-Steroidal Anti-Inflammatory drugs (NSAIDs) (for ≥7 days) may not be initiated during the study, but may be continued and dose adjusted as clinically indicated until the Week 44 visit. After the Week 44 visit any increase in the NSAID dose above the baseline (Day 1) or Week 44 dose, whichever is higher, will declare the participant as a treatment failure unless the NSAID is given for <7 days.

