Participants randomized to Arms A and B who enter the study on immunosuppressants will discontinue immunosuppressants at or prior to the Week 4 visit. Continuing the stable immunosuppressant dose until Week 4 allows participants to receive 3 weeks of belimumab SC prior to discontinuing their immunosuppressants. Corticosteroids may be adjusted as necessary during this transition period. If participants in Arms A and B receive immunosuppressants after the Week 4 visit they will be deemed treatment failures for the efficacy endpoints. Participants in Arm C who enter the study on stable immunosuppressants may continue their stable immunosuppressants throughout the study at the discretion of the investigator. If participants in Arm C require an addition of a new immunosuppressant after Week 12 they will be considered a treatment failure. See Section 7.7.1.4 for additional details on management of immunosuppressants.

After the initial 12 weeks of study treatment, a protocol-specified corticosteroid taper will be initiated and conducted under the direction of the investigator for participants in all 3 arms. The taper will proceed with a target of reaching a prednisone equivalent dose of ≤5 mg/day by Week 26. If the investigator believes the participant would benefit from continued steroid taper and, if tolerated, a prolonged corticosteroid taper should continue after Week 26 with the goal of corticosteroid discontinuation. Participants who are able to tolerate the final taper will be withdrawn from corticosteroids. If a participant is unable to tolerate the final stage of the corticosteroid taper, the investigator may reinitiate corticosteroids at a prednisone equivalent dose of up to and including 5 mg/day. If a 7-day average prednisone equivalent dose of >5 mg/day is required at any time after Week 26, the participant will be considered a treatment failure for the efficacy endpoints. The recommended corticosteroid taper scheme is described in Appendix 2.

Anti-malarial therapies for SLE may not be initiated during the study, but may be continued or dose-adjusted during the study, and will be allowed within the definitions of the efficacy endpoints.

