7.7.1.4. Other Immunosuppressant Agents

Belimumab SC 200 mg/week will be initiated in all treatment arms on Day 1 of the study. Participants who enter the study on immunosuppressant therapy in Arms A and B will continue their stable immunosuppressant regimen until up to Week 4. At or prior to the Week 4 visit, immunosuppressants will be discontinued. Corticosteroids may be adjusted as necessary during this transition period. Participants in Arm C may continue their immunosuppressant agents throughout the study.

Starting any new immunosuppressant agent after Day 1 for increased lupus disease activity will cause the participant to be declared a treatment failure. An immunosuppressant agent may however be replaced with one of the agents listed below due to documented toxicity or lack of availability.

For participants in Arms A and B, the dose of existing immunosuppressant agents may be adjusted, as clinically required, up to the Week 4 visit. Any existing immunosuppressant agents will be discontinued at or prior to the Week 4 visit for Arms A and B.

Participants in Arm C may continue their existing immunosuppressant agents throughout the course of the study. Dosage of existing immunosuppressant agents may be increased as clinically necessary until Week 12. After the Week 12 visit, any increase in dose over the baseline (Day 1) or Week 12 visit dose, whichever is higher, will cause the participant to be declared a treatment failure.

The common allowable maximum doses for immunosuppressant agents at baseline (Day 1) and during the study are listed below:

- Azathioprine 300 mg/day
- 6-mercaptopurine 300 mg/day
- Mycophenolate mofetil (PO)/ mycophenolate mofetil hydrochloride (IV) 4 g/day
- Mycophenolate sodium (PO) 2.88 g/day
- Methotrexate 25 mg/week
- Oral cyclophosphamide 2.5 mg/kg/day (Note: use not permitted in Germany)
- Cyclosporine 4 mg/kg/day*
- Tacrolimus 0.2 mg/kg/day*
- Sirolimus 2 mg/kg/day*
- Thalidomide 200 mg/day
- Leflunomide 40 mg/day*
- Mizoribine 150 mg/day

*Clinical loading dose is permitted when replacing immunosuppressant agents. Monitor blood levels as clinically indicated.

An immunosuppressant agent may be replaced with one of the agents above due to documented toxicity or lack of availability. For other immunosuppressant agents not listed above, the investigator must contact the Medical Monitor for approval.

New topical immunosuppressive agents (e.g., eye drops, topical creams) are allowed after Day 1.

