7.7.1.5. Nonsteroidal Anti-inflammatory Drugs (NSAIDs), Aspirin, and Acetaminophen

Since NSAIDs and aspirin may affect efficacy parameters (e.g., arthritis) and may affect renal function (NSAID nephropathy), the use of these agents should be initiated and stabilized prior to entry into the trial.

NSAIDs may be continued and dose adjusted as clinically indicated until 8 weeks before efficacy visits, i.e., Weeks 52, 64, and 104. During the intervals of 8 weeks before these efficacy endpoints, any increase in the NSAID dose above the dose at Day 1 or the visit day starting the interval of 8 weeks prior to these key efficacy visits, whichever is higher, will declare the participant as a treatment failure unless the NSAID is given for <7 days. The day of the Week 44, 56, and 96 visits will count as the start of these 3 intervals.

New NSAIDs may not be added after Day 1 unless given for <7 days. Initiation of an NSAID after Day 1 that is given \ge 7 days will declare the participant as a treatment failure.

An NSAID may be replaced with another NSAID due to documented toxicity or lack of availability.

Daily doses of aspirin up to 1000 mg/day are allowed at any time during the study. Daily doses of aspirin above 1000 mg/day may be initiated at any time up to the Week 44 visit and may continue through the end of the study. For participants who never received an aspirin regimen at a dose >1000 mg/day between the Day 1 and Week 44 visit, starting a new aspirin regimen at a dose >1000 mg/day after the Week 44 visit will declare the participant a treatment failure unless the aspirin is given for <7 days.

Acetaminophen (paracetamol) is primarily an analgesic and lacks the anti-inflammatory properties of other NSAIDs. The use of acetaminophen is recommended when possible to treat non-SLE related conditions, in the absence of a pre-existing hepatic function deficiency.

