5.10. Treatment Failures

Treatment failures are subjects meeting any of the criteria defined below, from the time they 1st met the criteria:

- Received a protocol prohibited medication
- Arm A&B: Received immunosuppressants after Week 4 rituximab infusion visit;
Arm C: Increased immunosuppressants (at a dose higher than at baseline and Week 12) after Week 12
- Arms A&B only: Received PI prescribed re-start belimumab medication after Week 52 visit and prior to Week 104 visit
- Started any new immunosuppressant after Day 1
- Received a prednisone equivalent corticosteroid 7-day average dose of >5 mg/day after Week 26 visit
- Received a dose above the allowable level or after a protocol specified timepoint (Section 7.7.1 of the protocol) prior to Week 52 visit

Further detail is provided in Section 15.6.15 Treatment Failure Rules During Study Conduct

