15.6.15.1. Summary

| Occurrence | Post Study Start Treatments | TX Failure: Arms A/B | TX Failure: Arm C |
|-----------------|--|----------------------|-------------------|
| After Day 1 | 
 NEW anti-malarial medication for SLE (other than for anti-malarial prophylaxis) NEW immunosuppressant medication Prohibited Medications and Non-Drug therapies | Yes | Yes |
| After Week 4 | 
 Immunosuppressant medication | Yes | No |
| After Week 12 | 
 Immunosuppressant medication dose increased over baseline (Day 1) or Week 12 visit dose, whichever is higher | Not Applicable | Yes |
| Week 27 onwards | 
 Corticosteroid (Prednisone equivalent) dose >5mg/day (Average day of assessment and 6 prior days) | Yes | Yes |

| Occurrence | Post Study Start Treatments | TX Failure: Arms A/B | TX Failure: Arm C |
|------------------|---|----------------------|-------------------|
| After Week 26 | 
 High Dose CS for Non-SLE use (Maximum use 7 days, taper [≤ 5 mg/day]. 21 days) | Yes | Yes |
| After Week 44 | 
 Aspirin doses >1000 mg days if never received such doses between Day 1 and Week 44 (Note: It does Not apply if given <7 days) | Yes | Yes |
| Weeks 44 to 52* | 
 NSAIDs (dose above Day 1 or the visit day starting the 8 weeks interval for ≥ 7 days) Intraarticular CS injections High Dose CS for Non-SLE use | Yes | Yes |
| After Week 52 | 
 IP – Belimumab SC | Yes | No |
| Weeks 56 to 64* | 
 NSAIDs (dose above Day 1 or the visit day starting the 8 weeks interval for ≥ 7 days) Intraarticular CS injection High Dose CS for Non-SLE use | Yes | Yes |
| Weeks 96 to 104* | 
 NSAIDs (dose above Day 1 or the visit day starting the 8 weeks interval for ≥ 7 days) Intraarticular CS injections High Dose CS for Non-SLE use | Yes | Yes |

*8 weeks prior to major efficacy assessments (Primary endpoint [Week 52] and major secondary endpoints [Weeks 64, 104]).

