15.6.15.2. SLE Medication Categories

| Medication Category | Rule |
|---------------------|--|
| Anti-malarials | Set to "ANTIMALARIALS" if the preferred term begins with "QUINACRINE", "QUININE", "HYDROXYCHLOROQUINE", "MEPACRINE", or "CHLOROQUINE" AND the route of administration is not 'TOPICAL', 'VAGINAL', 'CONJUNCTIVAL', 'INTRANASAL', 'INHALATION', 'INTRA-OCULAR', 'INTRATRACHEAL', 'EPIDURAL', 'INTRA-ARTICULAR', or 'OTHER'. |
| Steroids | Set to 'STERIODS' if at least one associated ATC code (ATCCD1 – ATCCD6) begins with 'H02' AND Route of administration is "INTRADERMAL", "INTRAMUSCULAR", "BUCCAL", "PARENTERAL" "INTRAVENOUS", "ORAL", "SUBCUTANEOUS", or "INTRA-ARTICULAR". |

| Medication Category | Rule |
|---------------------|--|
| Immunosuppressants | Set to 'IMMUNOSUPPRESSANTS' if at least one associated ATC code (ATCCD1 – ATCCD6) begins with 'L04A' or the preferred term begins with "CYCLOPHOSPHAMIDE" (oral and parenteral routes) or "MERCAPTOPYRINE" (oral route) AND route of administration is not "TOPICAL" or "OPHTHALMIC" AND not classified above as "ANTIMALARIALS". |
| NSAIDs | Set to NSAIDs if at least one associated ATC code (ATCCD1 – ATCCD6) begins with 'M01A'. Glucosamine and Chondroitin not considered NSAIDs |
| Aspirin | Set to "ASPIRIN" if CMDECOD contains "ACETYLSALICYLIC ACID" or "ACETYLSALICYLATE LYSINE". |
| Prohibited | Set to "PROHIBITED" if at least one associated ATC code (ATCCD1 – ATCCD6) begins with 'L04AB' or 'V98' or if any of the following conditions are met, if CMDECOD equals , "BELIMUMAB", "ADALIMUMAB", "ETANERCEPT", "INFLIXIMAB", "CERTOLIZUMAB", "TOCILIZUMAB", "GOLIMUMAB", "RITUXIMAB", "ABATACEPT", "ANAKINRA", "CANAKINUMAB", "USTEKINUMAB", "BRODALUMAB", "SECUKINUMAB", "IXEKIZUMAB", "EPRATUZUMAB", "TABALUMAB", "ATACICEPT", "IMMUNOGLOBULIN" (IV route), "CYCLOPHOSPHAMIDE" (IV route), or "PLASMAPHERESIS" |

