15.6.15.7. Nonsteroidal Anti-inflammatory Drugs (NSAIDs), Aspirin, and Acetaminophen

NSAIDs and aspirin should be initiated and stabilized prior to entry into the trial.

Baseline is defined as the NSAID/Aspirin received on the treatment start date (Day 1)

NSAIDs may be continued and dose adjusted as clinically indicated until 8 weeks before efficacy visits, i.e., Weeks 52, 64, and 104. During the intervals of 8 weeks before these efficacy endpoints, any increase in the NSAID dose above the dose at Day 1 or the visit day starting the interval of 8 weeks prior to these key efficacy visits, whichever is higher, will declare the participant as a treatment failure unless the NSAID is given for <7 days. The day of the Week 44, 56, and 96 visits will count as the start of these 3 intervals.

An NSAID may be replaced with another NSAID due to documented toxicity or lack of availability. Replacement due to toxicity/ lack of availability will be assessed during clinical adjudication.

New NSAIDs may not be added after Day 1 unless given for <7 days. Initiation of an NSAID after Day 1 that is given ≥ 7 days will declare the participant as a treatment failure.

NSAIDs with an administration route of ‘TOPICAL’ or ‘CONJUNCTIVAL’ will not be considered as TF’s.

Aspirin will not be considered in the NSAID TF rules.

Daily doses of aspirin up to 1000 mg/day are allowed at any time during the study. Daily doses of aspirin above 1000 mg/day may be initiated at any time up to the Week 44 visit and may continue through the end of the study. For participants who never received an aspirin regimen at a dose >1000 mg/day between the Day 1 and Week 44 visit, starting a new aspirin regimen at a dose >1000 mg/day after the Week 44 visit will declare the participant a treatment failure unless the aspirin is given for <7 days.

Daily doses of aspirin above 1000 mg/day may not be initiated in the 8 weeks before Week 64 and 104. The same rules as at Week 44 will be applied at Weeks 56 and 96

ACETYLSALICYLATE LYSINE (in mg) will be converted to standardised dose by multiplying by 0.556.

Acetaminophen (paracetamol) is primarily an analgesic and lacks the anti-inflammatory properties of other NSAIDs. The use of acetaminophen is recommended when possible to treat non-SLE related conditions, in the absence of a pre-existing hepatic function deficiency.

PRN use of NSAIDs or Aspirin will be identified as a potential TF and reviewed on a by subject review basis.

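### Summary and overview passages contradict the detailed treatment-failure rules for NSAIDs and new immunosuppressants, so some participants' response status depends on which passage is followed

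*SAP*

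**What the plan says.** The detailed sections are consistent. On NSAIDs, SAP 15.6.15.7 repeats protocol 7.7.1.5: "New NSAIDs may not be added after Day 1 unless given for <7 days", with longer use counted as failure. Both allow dose changes outside set intervals: "NSAIDs may be continued and dose adjusted as clinically indicated until 8 weeks before efficacy visits, i.e., Weeks 52, 64, and 104". Inside those intervals, failure means exceeding the higher of the Day 1 dose and the dose at the visit that opens the interval. On immunosuppressants, SAP 15.6.15.6 repeats protocol 7.7.1.4: "Starting any new immunosuppressant agent after Day 1 for increased lupus disease activity will cause the participant to be declared a treatment failure".

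Five other passages differ:

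- (a) The SAP 15.6.15.1 table lists NSAIDs only in the rows for Weeks 44-52, 56-64 and 96-104, as "NSAIDs (dose above Day 1 or the visit day starting the 8 weeks interval for" seven days or more. Its row for events after Day 1 covers antimalarials, immunosuppressants and prohibited therapies, but not NSAIDs. It also drops the higher-of-the-two qualifier.
- (b) The protocol synopsis fails "After the Week 44 visit any increase in the NSAID dose above the baseline (Day 1) or Week 44 dose, whichever is higher", unless given for under seven days, and sets no end to the period.
- (c) SAP 5.10 lists as failure: "Received a dose above the allowable level or after a protocol specified timepoint (Section 7.7.1 of the protocol) prior to Week 52 visit". SAP 15.6.15 instead runs to whichever analysis visit is being assessed, naming Weeks 52, 64 and 104.
- (d) Protocol 5.1 states: "If participants in Arm C require an addition of a new immunosuppressant after Week 12 they will be considered a treatment failure". Protocol 7.7.1.4 and the SAP start from Day 1.
- (e) SAP 15.6.15.2 identifies 6-mercaptopurine by a preferred term that begins with "MERCAPTOPYRINE".

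**The concern.** Under SAP 7.1.1 a responder must not have been a treatment failure at the current or any earlier visit, so one early event carries forward to Weeks 52, 64 and 104. If two passages classify the same event differently, the endpoint is not uniquely defined for that participant.

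SAP 15.6.15.3 sends potential violations to adjudication after a program has output them. A program written from the summary table would not output a short NSAID course at Week 20. A match on the misspelled term would not output mercaptopurine. The same string could also affect the baseline immunosuppressant covariate, which SAP 5.5.1 derives from reported medications. Neither SAP addendum corrects these passages. The first addendum (section 2.8) does note the dictionary spelling of another immunosuppressant, ciclosporin, but not this one.

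**Working it through.** **Step 1. Apply each text to test cases.** NSAID events last at least seven days.

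| Event | Detailed rules | Conflicting passage |
|---|---|---|
| New NSAID at Week 20 for 10 days | Failure at Weeks 52, 64, 104 | SAP 15.6.15.1 table: not a failure at any |
| NSAID used at Day 1, raised at Week 30, then held | Not a failure (does not exceed the Week 44 dose) | Same table, read literally: above the Day 1 dose, so a failure |
| NSAID increase at Week 46 | Failure at all three | None: table and synopsis agree |
| NSAID increase at Week 54 | Not a failure | Synopsis: failure at Weeks 64 and 104 |
| NSAID increase at Week 70 | Not a failure | Synopsis: failure at Week 104 |
| Joint injection at Week 60 | Failure at Week 64 (protocol 7.7.1.2, SAP 15.6.15.4) | SAP 5.10 as worded: not covered, being after Week 52 |
| New immunosuppressant for lupus activity at Week 8, Arm C | Failure | Protocol 5.1: not a failure |
| Oral mercaptopurine | Immunosuppressant | SAP 15.6.15.2 string as printed: no match |

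Item (b) cannot change Week 52, because the synopsis and the detailed text agree for Weeks 44-52. Item (c) likewise concerns only Weeks 64 and 104. Item (d) concerns Arm C only.

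**Step 2. Reproduce the plan's power.** Protocol 10.2 gives 70 and 140 participants, rates of 10% and 35%, and 5% two-sided significance.

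- Pooled rate = (7 + 49)/210 = 0.2667.
- SE under the null = √[0.2667 × 0.7333 × (1/70 + 1/140)] = 0.0647.
- SE under the alternative = √[0.10 × 0.90/70 + 0.35 × 0.65/140] = 0.0540.
- z = (0.25 − 1.96 × 0.0647)/0.0540 ≈ 2.28, so power is 98.9%. The plan states at least 98%.

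**Step 3. Size of the new-NSAID omission.** Let f be the share of Arms A and B with an NSAID course that the detailed text fails and the table misses. The documents give no f. Assume 5%, range 2-10%, equal in both arms, with response at the planning rates.

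- Would-be responders affected = 140 × f × 0.35 + 70 × f × 0.10.
- f = 5%: 2.45 + 0.35 = 2.8. f = 2%: 0.98 + 0.14 = 1.1. f = 10%: 4.9 + 0.7 = 5.6.
- Shift in the difference = f × (35 − 10) points = 1.25 (0.5 to 2.5).
- Power with rates reduced to 9.5% and 33.25% (f = 5%) is 98.3%. At 9% and 31.5% (f = 10%) it is 97.6%.

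**Step 4. Near the decision boundary.** With 7/70 in control, the likelihood-ratio test gives p = 0.044 at 29/140 and p = 0.057 at 28/140. The former is a difference of 20.7 − 10.0 = 10.7 points, consistent with the plan's 11% minimum detectable effect. One reclassified responder could decide significance there.

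**The case against.** The best defence is that the documents have a hierarchy. The endpoint definitions cite SAP 15.6.15, which points to protocol 7.7, and SAP 5.10 refers on to 15.6.15. The table is headed as a summary, and no passage says that a new NSAID is not a failure. SAP 15.6.15.7 contains the new-NSAID rule and reads like the programming text. This largely stands: the operative rules agree. It does not remove the contradictions, because the table, SAP 5.10 and the match string are all text a programmer could implement as written.

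Four stronger readings are tempting but unsupported:

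- An NSAID started at Week 20 and continued past Week 44 might seem to escape the table. Read literally, it is above a zero Day 1 dose in Weeks 44-52, so the table arguably catches it. The clear conflict is a course that ends before Week 44.
- At f = 5%, about 10 of 210 participants might seem to have an uncertain Week 52 result. Only about 3 would otherwise be responders; the rest are non-responders either way.
- The Arm C conflict might seem to touch the confirmatory test. That test uses Arms A and B only (SAP 7.1.1), and protocol 5.1 itself refers to 7.7.1.4.
- Mercaptopurine might be said to go unflagged. That depends on program code the documents do not show. The SAP names the drug separately from its ATC group rule, which suggests the group was not relied on to catch it, but the code is not given.

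Review is also not wholly confined to program output: SAP 15.6.15.8 routes some events found through monitoring to failure review. That provision concerns investigational agents and co-enrolment, not NSAIDs.

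**Conclusion.** The contradictions are real. Following the SAP 15.6.15.1 table, SAP 5.10 or the printed match string literally would misapply a component of the primary or major secondary endpoints. Items (a) and (e) can reach Arms A and B at Week 52; (b) and (c) reach Weeks 64 and 104 only; (d) reaches only the exploratory Arm C comparison.

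For the new-NSAID omission alone, the effect is about 1 to 6 would-be responders (about 3 at 5%) and 0.5 to 2.5 points of a planned 25. This rests on an assumed 2-10% frequency and on planning-rate response among those participants. Under those assumptions it is an upper bound, because courses continued into Weeks 44-52 may be caught by the table. The other items are not quantified.

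A reader might infer that the failure rules as a whole are incompatible, or that reported results are wrong. The documents support neither: the detailed rules match, the power figure reproduces, and how the program was written is unknown.

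**What to change.** State each failure rule once (NSAID start, NSAID increase and the weeks it covers, and new immunosuppressant in Arm C and from which visit), and have the synopsis, protocol 5.1, SAP 5.10 and the SAP 15.6.15.1 table refer to it. Which clinical rule applies is for the sponsor to decide; the passages must be reconciled either way. Align the time limit in SAP 5.10 with SAP 15.6.15. Correct the mercaptopurine string in SAP 15.6.15.2.

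Then confirm that the failure program follows the reconciled rules, rerun the listing, adjudicate newly flagged records blind, and report how many Week 52, 64 and 104 classifications change. The second SAP addendum says the primary analyses have been done, so any changed Week 52 classification should be shown openly beside the reported result.

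The cost is wording changes, one program rerun and adjudication of a probably small set of records. Protocol Appendix 4 already provides an adjudication team that stays blinded until the end-of-study database freeze.
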